## B. Exposure definition

The primary exposure of interest is new (incident) initiation of systemic DEX. DEX exposure is defined with procedure codes (current procedural terminology, CPT-4/healthcare common procedure coding system, HCPCS [*CMS 2020(b)*]), hospital charge codes for the corresponding text strings (e.g., 'dexamethasone', 'decadron'), and drug names referenced from national drug codes (NDC), where there is an absence of evidence of a non-systemic route of administration (e.g., ciprofloxacin 0.3%/dexamethasone 0.1% ear drops are excluded). All available data types with treatment-specific information are used for assessment of DEX exposures, including medical claims, pharmacy claims, and chargemaster records. DEX use is considered "new" if the patient had no record of systemic DEX dispensing or remaining outpatient pharmacy supply during the 90-day *Treatment Washout Window* prior to the cohort entry and up until 1 day prior to treatment index (Day 0, hospital admission date).

## C. Study population

### 1. Cohort entry

#### Hospitalized Patients with COVID-19:

Patients will enter the cohort upon the admission date of the first qualifying inpatient hospitalization observed in the hospital chargemaster data. The first eligible cohort entry date is **01-April-2020**, the date when the ICD-10 code for COVID-19 diagnosis was added. The last possible cohort entry date will be 60 days prior to the last date of available data [see *Appendix A.5 Exploration 5* for additional detail justifying this design decision].

COVID-19 confirmation was defined as either of the following occurring between 21 days prior to the hospital admission date and the treatment index date, which is described in section C.2. below (inclusive; **Day -21 to Day T**):

- Outpatient medical encounter prior to or on the admission date or diagnosis 'present at admission' with ICD-10-CM diagnosis of U07.1 for COVID-19, virus identified; OR
- positive or presumptive positive SARS-CoV-2 diagnostic laboratory test result

The decision to include either diagnosis or positive laboratory test results was based on an initial exploration [see justification detail in *Appendix A.1. Exploration 1*].

For the DEX+ versus MPRED+ comparison (**Secondary Objective II**), given the increased use of MPRED earlier on in the COVID-19 pandemic, we may consider delaying the cohort entry to start in May or June pending data exploration.

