### A. Study design

This study is an observational cohort study using secondary healthcare data. The study diagram and its components are illustrated and further detailed below [*see Figure 2*].

Figure 2. Study diagram

Inclusion/Exclusion Criteria	
COVID-19 confirmation	Hospitalized patients with confirmed COVID-19 (ICD 10 diagnosis: U07.1 or positive or presumptive positive SARS-CoV-2 diagnostic laboratory test result; Day -21 to Day T).
Baseline Exclusion	Exclude patients without activity in the 183 day baseline period (Day -183 to Day -1).
Missing Demographics Exclusion	Exclude patients with missing age, sex, or region on the hospital admission date (Day 0; CED).
COVID-19 Vaccine Exclusion	Exclude patients with any record of a COVID-19 vaccine on or any time prior to the treatment index date given that these patients are assumed to be selectively different (Day S to Day -1).
Treatment Exposure	Hospitalized COVID-19 patients with new use of systemic dexamethasone (DEX+) or referent groups (CSI-, DEX-, MPRED+). Treatment index date (Day T) must occur between hospital admission date (Day 0; CED) and 1 day prior to hospital discharge date (Day D-1).
Treatment Washout	Exclude patients with prior systemic CSI use from all comparisons (Day -90 to Day T-1).
Covariate Assessment	
Baseline	Baseline (pre-admission) comorbidities, co-medications, and healthcare resource utilization (HCRU; Day -183 to Day -1).
Pre-admission	COVID-19-related symptoms, complications, and HCRU leading up to the hospital admission date (Day -21 to Day -1).
On admission	Demographics, facility characteristics, and covariates related to admitting status (Day 0; CED).
Pre-treatment (Inclusive)	Treatments administered prior to or concurrent with treatment index date, pre-treatment clinical status, and time from admission to treatment (Day 0 to Day T).
mWHO Severity	COVID-19 severity per modified version of WHO ordinal scale (mWHO), used for matching and subgrouping of DEX+ and referent patients (Day T-1 to Day T).
Outcome Assessment	
Follow-up	Follow-up window for primary outcome of 28-day inpatient mortality (Day T+1 to the earlier of Day T+28 or D).

*CED, Cohort Entry Date; D, Hospital discharge date; S, Start of available data; T, Treatment index date*

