### 2. Treatment index

#### **Primary Objective -- New users of DEX (DEX+) versus matched non-users of CSI (CSI-):**

From the patients who enter the cohort, new users of DEX between the admission date (*Day 0*) and 1 day prior to discharge date (*Day D-1*) or a maximum period of 21 days after admission (*Day 21*) will be selected. Greater than 80% of the patients who initiated DEX did so within 1 or 2 days of their hospitalization. A sensitivity analysis (SA2) will be conducted to explore initiation dates further. For each new user of DEX, at least 1 patient who has not (yet) used any CSI as of the DEX patient's index date or within the 90-day washout period prior matched on the

criteria defined in Table 2 below will be randomly risk-set sampled (RSS). DEX+ versus CSI-matching ratios of 1:1, 1:2, 1:3, and 1:4 will be considered to select up to 4 non-user referent patients for each exposed, and the ideal ratio will be selected based on the diagnostic criteria [defined below in section *VI.B. Diagnostic phase and checklist*].

RSS matching allows us to proxy the ‘standard of care’ by randomly selecting 1 or more patients who have not initiated DEX from the risk set of patients who are eligible for initiating DEX at the same time [*Li 2001*]. Since the COVID-19 pandemic and treatment of patients with COVID-19 is rapidly changing over time, there is much potential for calendar-time bias. Furthermore, patients prescribed DEX may appreciably differ from those not prescribed DEX. Employing an RSS that matches DEX users and non-users on the date of DEX treatment (in the users) and time since admission will minimize the potential for this bias. Cohort entry month will also be included in the propensity score (PS) calculation to further adjust for time-related biases. Geographic region was considered for the RSS matching criteria. However, during our data explorations, the comparison of baseline balance showed that matching without region yielded better baseline balance than matching with region. Therefore, we removed region from the RSS matching. However, given known regional differences, we still account for region in our propensity score model.

The *treatment index date* (Day T) for patients who are users and for the matched non-user referent patients will be defined by the index date of the matched users.

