### **Secondary Objective II -- New users of DEX (DEX+) versus new users of MPRED (MPRED):**

From the patients who enter the cohort, all patients who begin use of DEX or MPRED between the admission date (*Day 0*) and 1 day prior to discharge date (*Day D-1*) or a maximum period of 21 days after admission (*Day 21*). New use will be determined using a 90-day washout period to exclude patients with prior use of either DEX or MPRED during the 90 days prior. If a patient uses both treatments over the course of the admission, they will be assigned to their first qualifying treatment arm. If a patient receives both DEX and MPRED on the treatment index, they will be excluded since the effects or the drugs cannot be disentangled among these patients.

*Table 2: Risk set sampling (RSS) matching criteria*

RSS matching criteria	Variable type	Categories (for categorical) / calipers (for continuous)
Calendar date	continuous	±3 days
Age	continuous	±3 years
Sex	categorical	male, female
Combined comorbidity score over 183d baseline period [ Gagne 2011 ]	categorical	0-1, 2-3, 4-5, 6+
Time since hospital admission	categorical	0-1, 2-3, 4-5, 6 - 9, 10 - 14, 15 - 19, 20+ days
COVID-19 severity at treatment index date, per modified WHO (mWHO) score	categorical	No O2, O2/NIV, IMV (highest recorded from days T-1 to T) [see additional subgroup detail below in section V.D. Subgroups ]

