
Pre-admission Covariates (Day -21 to Day -1)
	
COVID-19 symptoms and HCRU prior to the admission date.
	
 
- COVID-19 symptoms: pre-admission COVID-19 symptoms
 
- HCRU: Inpatient hospitalization, emergency room encounter
 

Admission Covariates (Day 0; CED)
	
Demographics, hospital facility characteristics, and COVID-19 severity on the admission date.
	
 
- Hospital and admitting characteristics: Hospital setting type, hospital teaching status, hospital number of beds, admission source, emergency room encounter, ambulance encounter, admission type
 
- COVID-19 severity at admission: mWHO severity categorization on the admission date
 

Pre-treatment Covariates (Day 0 to Day T, inclusive)
	
Treatments administered prior to or concurrent with treatment index date, pre-treatment clinical status, and time from admission to treatment.
	
 
- Pre-treatment COVID-19 status: Highest recorded mWHO severity
 
- Pre-treatment utilization characteristics: Number of days hospitalized, number of days with critical/ICU care, in ICU at treatment index, number of unique department codes, number of unique procedure codes
 
- Demographics: Month of treatment index, age, sex, insurance type, US region
 

*\*Smoking/tobacco use may be under-reported [see section VIII. Limitations for additional detail]*

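### Days from first COVID-19 record to treatment index can span weeks, but are neither matched, nor listed as a propensity score covariate, nor named for the balance check.

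*Protocol*

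**What the plan says.** Section V.C.1 defines confirmation as "either of the following occurring between 21 days prior to the hospital admission date and the treatment index date". There are two routes. The diagnosis route is limited to "Outpatient medical encounter prior to or on the admission date or diagnosis 'present at admission", so in practice it falls between about Day -21 and Day 0. The laboratory route runs to Day T. Section V.C.2 allows the index date up to "a maximum period of 21 days after admission".

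The time variables used afterwards count from admission or follow the calendar:

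- Table 2 matches on calendar date and on "Time since hospital admission" in the bands "0-1, 2-3, 4-5, 6 - 9, 10 - 14, 15 - 19, 20+ days".
- The covariate summary under Figure 2 names "pre-treatment clinical status, and time from admission to treatment (Day 0 to Day T".
- Table 3 lists "Number of days hospitalized, number of days with critical/ICU care, in ICU at treatment index" and the month of treatment index.

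No table counts days from diagnosis, test or symptom onset. Table 4, row 3 applies its balance rule (absolute standardized difference, ASD, of at most 0.10) to potential confounders, and this interval is not listed as one. None of the sensitivity analyses SA1 to SA8 addresses it: SA2 restricts hospital time but leaves the 21-day lead, and SA4 widens the confirmation window. The limitations in Section VIII do not mention it.

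**The concern.** Stage of illness plausibly influences both whether dexamethasone is started and whether the patient dies in the next 28 days. Patients well past confirmation may be recovering, or may be in hospital for another reason. Those confirmed at admission may still be worsening.

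Time since admission cannot separate these patients well. Section V.C.2 states: "Greater than 80% of the patients who initiated DEX did so within 1 or 2 days of their hospitalization". Hospital time therefore varies little for most exposed patients, and much of the variation in time since confirmation can lie in the three weeks before admission. Risk-set sampling aligns calendar time and hospital time, but not time in the disease. If the arms differ in illness stage within matched strata, the hazard ratio carries confounding that no listed diagnostic measures directly.

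**Working it through.** The protocol states no figure for this interval, so there is nothing to reproduce. Three checks follow.

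**1. Largest gap between two patients in one matching band.** Inputs: confirmation from Day -21 (V.C.1), index up to Day 21 (V.C.2), bands from Table 2. For a band running from *lo* to *hi*:

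- Diagnosis route, where the later patient is confirmed on Day 0: gap = (hi + 21) - lo.
- Laboratory route, where the later patient is confirmed on Day T: gap = hi + 21.

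| Band (days) | Diagnosis route | Laboratory route |
|---|---|---|
| 0-1 | 22 | 22 |
| 2-3 | 22 | 24 |
| 4-5 | 22 | 26 |
| 6-9 | 24 | 30 |
| 10-14 | 25 | 35 |
| 15-19 | 25 | 40 |
| 20+ (to Day 21) | 22 | 42 |

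These are maxima for a pair of patients, not differences between arms.

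**2. What the existing balance check could hide between arms.** If early-confirmed patients all have a 21-day lead, a 7-day difference in arm means needs a difference of 7/21 = 33 percentage points in the share confirmed early. A 14-day difference needs 14/21 = 67 points.

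Now suppose that one pre-admission proxy with prevalence *q* just meets ASD 0.10, and that its frequency differs by *d* between early-confirmed and other patients. Then:

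hidden difference in share = 0.10 × √(q(1 - q)) / d; hidden mean gap = that share × lead time.

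The values of *q*, *d* and the lead time are assumptions; the documents give none.

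- q = 0.1, d = 0.5: 0.10 × 0.30 / 0.5 = 0.06, or 0.4 days with a 7-day lead and 1.3 days with a 21-day lead.
- q = 0.5, d = 0.2: 0.10 × 0.50 / 0.2 = 0.25, or 1.8 days with a 7-day lead and 5.2 days with a 21-day lead.
- d = 0.1, a nearly uninformative proxy, 21-day lead: 6.3 days at q = 0.1 and 10.5 days at q = 0.5.

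**3. Effect on the estimate, for illustration only.** Let *a* and *b* be the late-stage shares in the dexamethasone and referent arms, and *k* the death-risk ratio for late versus other stage. Bias factor = (1 - a + ak) / (1 - b + bk).

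- a = 0.05, b = 0.15: 0.975/0.925 = 1.05 for k = 0.5; 1.025/1.075 = 0.95 for k = 1.5.
- a = 0.10, b = 0.30: 0.95/0.85 = 1.12 for k = 0.5; 1.05/1.15 = 0.91 for k = 1.5.

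These shares and ratios are assumed, and the sign depends on *k*. The formula also ignores the matching on severity. Its use is to show detectability: the two share differences correspond to ASDs of 0.10/√0.0875 = 0.34 and 0.20/√0.15 = 0.52. Row 3 would flag both if the variable were listed.

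**The case against.** A reader might infer that time since admission is the only thing controlled. The protocol does not support that. Table 2 also matches on respiratory severity from T-1 to T. Table 3 lists dyspnea or hypoxia, pneumonia, ARDS, shock and organ failure before admission and before treatment, as well as pre-admission symptoms, emergency and inpatient use, and severity at admission. These bear on illness stage, and they fall under the balance check.

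A reader might also infer that whole arms could be weeks apart while every check passes. That turns a pairwise maximum into a mean difference. The second check shows that it would need proxies carrying almost no information.

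A third tempting reading is that patients first confirmed late in their stay drive the problem. First confirmation after admission requires a positive test. In Exploration 1 only 0.5% had a laboratory result alone and 8.8% had both result and code; in Table A.2 the positive-result shares are 3.9% and 3.5%.

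It can further be said that the record date is not onset, that open claims may miss earlier records, and that Section VIII.A concedes residual confounding in general terms.

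All of this stands and narrows the point, but it does not remove it. Current severity is not stage: a patient without oxygen may be early and worsening or late and recovering. Section VIII.A says that this category rests on the absence of records and that day-level diagnoses are lacking. The listed symptoms carry no stated onset date. The positive-test covariate says little about timing, because 1,730/1,840 (94.0%) and 1,735/1,840 (94.3%) of the exploratory matched arms had no test recorded.

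**Conclusion.** The gap is real but moderate. The protocol uses the confirmation date for eligibility and then leaves days since confirmation out of matching, the covariate list, the named balance items, the sensitivity analyses and the limitations. Pairs in the 0-1 day band can be 22 days apart.

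Between arms, a residual of about 0.4 to 5 days is what the assumed, moderately informative proxies would leave. Larger gaps need nearly uninformative ones. The documents give no distribution of the interval by arm, so neither the size nor the direction of any bias in the hazard ratio can be derived, and the bias factors above are not estimates. The conclusion also assumes that the record date tracks illness stage at least roughly. Nothing here shows that the planned estimate is wrong; it shows that a plausible confounder can go unexamined although the data to examine it are already in hand.

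**What to change.** Derive days from the first qualifying record (U07.1 or positive test) to Day T, in categories such as 0-1, 2-4, 5-7, 8-14 and 15+. Add the variable to the Table 3 propensity score covariates, name it in Table 4, row 3 for all three comparisons, and report its distribution by arm. Placing it in Table 3 rather than Table 2 avoids thinning the risk sets and also covers the methylprednisolone comparison, for which no risk-set sampling is described. A separate flag for first confirmation after Day 1 is optional, since that route appears to be rare.

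If the interval is also checked as a continuous variable, ASD ≤ 0.10 holds the arm difference to 0.1 SD. With an assumed SD of 3 to 8 days, that is about 0.3 to 0.8 days.

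The cost is one derived variable. It is an imperfect proxy for onset, open claims may miss some pre-admission records and so understate the interval, and for patients first confirmed at admission it repeats time since admission. These limits belong in Section VIII.

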	SA4: Broaden patient population to include patients with confirmed COVID after treatment index*	
Detail: Additionally include patients with positive or presumed positive lab values or COVID-19 diagnosis occurring anytime during hospitalization, including discharge diagnoses.
 
Purpose: Evaluate whether HR is robust within a broader cohort including people without a COVID-19 diagnosis prior to or at admission. Will increase the sample size by approximately 10%, but may have the potential for misclassification of patients who were hospitalized for reasons other than COVID-19 who had a secondary diagnosis of COVID-19 or contracted COVID-19 during hospitalization as patients hospitalized for COVID-19.

Category	Brief Description	Detail / Purpose
Follow up censoring	SA5: Broaden the follow-up period for capturing inpatient mortality endpoints*	
Detail: Determine whether treatment with DEX reduces the risk of inpatient mortality within 60 days during the initial hospitalization.
 
Purpose: Evaluate effect of DEX on risk of inpatient death over a longer time frame. Aligns with mortality endpoint definition used in dexamethasone-ARDS trial [Villar 2020].

Additional subgroup	SA6: Stratify by ICU at Treatment index	
Detail: Estimate HR within ICU subgroup, defined based on the presence of a medical encounter with a revenue or department code indicating ICU at treatment index.
 
Purpose: Evaluate whether patients who initiate treatment while in the ICU differ from those who do not (within the overall cohort), an alternative proxy for COVID-19 severity.

Alternative subgroup definition	SA7: Define COVID-19 severity based on procedures alone	
Detail: Estimate HR within each of the mWHO subgroups using an algorithm that relies on procedural encounters only for defining O2/NIV and IMV (without the additional diagnostic encounters included in the primary definitions).
 
Purpose: Evaluate the impact of the robustness of findings among patients identified as O2/NIV and IMV and those identified as having neither (no O2) and understand the impact of the shift from lower to higher COVID-19 severity on the effect of DEX+ on 28-day mortality.

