## VIII. POTENTIAL LIMITATIONS

### A. Addressed in Design and Analyses

The following limitations have been addressed via study design or analyses, but will still be taken into consideration when interpreting and disseminating the findings from the implementation of this protocol:

- **Difficulty determining COVID-19 severity for the modified WHO categorization:** Oxygen supplementation is critical to the mWHO COVID-19 severity categorization (IMV, O2/NIV, no O2) upon admission and upon treatment initiation. Although it seems IMV is generally well captured via procedural claims data alone, it is unclear if oxygen support is fully captured via procedural claims. We have developed algorithms to determine IMV or O2/NIV support based on the presence of relevant procedures or diagnoses, but determination of no O2 will rely on the absence of recorded procedures or diagnoses for IMV or O2/NIV, which may increase the potential for misclassification in the no O2 group. Furthermore, given the lack of day-level diagnostic information (i.e., only admitting and discharge diagnoses are available), there is potential for under-reporting of severity on days during the hospital stay. Lastly, reporting of ARDS used to define IMV might not have been as well captured early in the pandemic, so there is increased potential for misclassification among patients hospitalized earlier in the study period. The inclusion of ECMO in the IMV definition may minimize the potential for under-report of ARDS since ECMO has been given as a short-term rescue therapy in patients with ARDS. In SA1, we restrict cohort entry to on or after June 16, 2020, given the release of the RECOVERY results in early June 2020 [see *section VII. Sensitivity Analyses, SA1*]. Through this analysis, we will be able to see how ARDS is reported among patients after the early months to better understand this concern. Further, SA7 allows us to evaluate the impact of the shift from lower to higher COVID-19 severity on the effect of DEX+ on 28-day mortality using an algorithm that relies on procedural encounters only for defining O2/NIV and IMV [see *section VII. Sensitivity Analyses, SA7*].

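### The primary cohort does not require COVID-19 to be the reason for admission, and no listed covariate or balance check records that reason directly

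*Protocol*

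**What the plan says.** **Entry to the primary cohort (section V.C.1).** A stay qualifies by a U07.1 code, from an "Outpatient medical encounter prior to or on the admission date or diagnosis" flagged as present at admission, or by a "positive or presumptive positive SARS-CoV-2 diagnostic laboratory test result". The window runs "between 21 days prior to the hospital admission date and the treatment index date". Under section V.C.2 the index date can fall up to "a maximum period of 21 days after admission". Diagnosis position is not mentioned, and neither this section nor the exclusions in V.C.3 refer to the reason for the stay.

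**Where other-reason stays are discussed.** Table 5 (SA4), repeated in Appendix B, warns that adding patients confirmed after index may bring in "patients who were hospitalized for reasons other than COVID-19 who had a secondary diagnosis of COVID-19", as well as patients infected in hospital. No matching statement is made for the primary cohort. The COVID-19 diagnosis item in VIII.A and Exploration 1 deal with code adoption and specificity.

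**Covariates and checks.** The hospital and admitting characteristics at Day 0 in Table 3 are "Hospital setting type, hospital teaching status, hospital number of beds, admission source, emergency room encounter, ambulance encounter, admission type". Admitting diagnosis is not named there, in the risk-set matching criteria (Table 2) or in the balance criterion (Table 4, row 3). Section VIII.A says of the inpatient data that "only admitting and discharge diagnoses are available"; section V.D says much the same of the chargemaster.

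**The concern.** Someone admitted for surgery, trauma, delivery or an unrelated medical problem who also carries a COVID-19 code or positive test may be less likely to start dexamethasone than someone admitted with COVID-19 pneumonia. That person's risk of dying in hospital may also differ. Reason for admission is then a common cause of treatment and outcome, known on Day 0.

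If other-reason stays are more frequent among the matched CSI- patients than among DEX+ patients, part of the primary hazard ratio compares reasons for admission. Every listed covariate could still meet the limit of 0.10 on the absolute standardized difference (ASD), because this variable is not among those tested.

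**Working it through.** The protocol states no figure on this point, so there is none to reproduce. The check has four steps.

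**1. Which stays can enter.**
- An outpatient U07.1 record up to 21 days before admission, even if the infection did not cause the admission.
- U07.1 present at admission, with no position requirement.
- A positive test between admission and the index date, which can include infection acquired in hospital. Exploration 1 suggests this route is small: 8.8% had both code and positive test and 0.5% the test only, so at most 8.8 + 0.5 = 9.3% had any positive test on record, in an earlier cohort and with no split by timing.

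The protocol does not count stays admitted for other reasons by any route.

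**2. What already adjusts for it.** Table 3 includes pneumonia, dyspnea or hypoxia, ARDS, shock, organ failure, a positive test, COVID-directed drugs up to and including Day T, pre-admission symptoms, admission type and source, severity at admission and ICU at index. Severity at index is also a risk-set matching factor, and its definition uses hypoxia and ARDS diagnoses. These are substantial proxies. They separate least among No-O2 patients with none of these records, where a mild COVID-19 admission and an unrelated admission look alike. In the exploration cohort (Table A.3) No-O2 patients were 1,098/1,840 = 59.7% of DEX+, against 501/2,104 = 23.8% of the dexamethasone arm in the cited UK trial. Under-recorded oxygen could also explain that gap, so it does not measure other-reason stays.

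**3. Possible size.** Let *a* and *b* be the shares of other-reason stays in matched DEX+ and CSI-, and *k* their death risk relative to COVID-19 admissions. If the treatment effect is the same in both kinds of stay, the estimated ratio is multiplied by

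(1 − a + a·k) / (1 − b + b·k)

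All values of a, b and k are assumptions.

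| a | b | k | Calculation | Factor |
|---|---|---|---|---|
| 5% | 10% | 0.3 | 0.965 / 0.930 | 1.04 |
| 5% | 10% | 2 | 1.050 / 1.100 | 0.95 |
| 5% | 20% | 0.3 | 0.965 / 0.860 | 1.12 |
| 5% | 20% | 2 | 1.050 / 1.200 | 0.88 |
| equal | equal | any | same / same | 1.00 |

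At the widest setting the planning hazard ratio of 0.80 would appear as 0.80 × 1.122 = 0.90 or 0.80 × 0.875 = 0.70.

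The formula is for risk ratios. As a check on the hazard scale, take no true effect, a 28-day risk of 15% in COVID-19 stays and 3% in others (k = 0.2), and shares of 5% and 20%. The arm risks are 0.95 × 0.15 + 0.05 × 0.03 = 0.144 and 0.80 × 0.15 + 0.20 × 0.03 = 0.126. The approximate hazard ratio is ln(0.856)/ln(0.874) = 1.155, against 0.144/0.126 = 1.143 for risks. The choice of scale matters little here.

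**4. Would the planned check show such an imbalance?** For a binary variable, ASD = |a − b| / √{[a(1 − a) + b(1 − b)]/2}.
- 2% vs 5%: 0.03/0.183 = 0.16
- 5% vs 10%: 0.05/0.262 = 0.19
- 5% vs 20%: 0.15/0.322 = 0.47

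Each exceeds 0.10, so the check would detect these imbalances if the variable were included.

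**The case against.** The strongest reply is that section III targets patients hospitalized with COVID-19 diagnosis or infection, not patients hospitalized for it. A reader might infer that the cohort is misdefined or contaminated. The documents do not support that: these stays fall within the target population, and their number is unknown. This part of the objection stands in full.

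A reader might also infer that the SA4 text is wrong. It describes the cost of adding diagnoses made after index and does not claim that the primary cohort is free of such stays. It needs no correction.

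The proxies are also strong, and a 5% versus 20% gap surviving balance on all of them is not demonstrated. That stands against the upper end of the range, but does not show that the proxies suffice in the No-O2 group.

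It is also fair that a usable admitting-diagnosis field is not established. Sections V.D and VIII.A say when diagnoses are recorded, not how complete they are, and the chargemaster element list that section IV places in Appendix C is not in the document at hand. The fix must therefore depend on completeness.

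The protocol requires balance on all potential confounders, allows automated variable selection and concedes residual confounding. None of these commits it to examining reason for admission.

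**Conclusion.** The point holds as an inexpensive improvement, not as an error in the plan. A plausible common cause of dexamethasone use and in-hospital death, probably available at Day 0, is adjusted for only through proxies and is never tabulated or checked.

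That the primary hazard ratio is biased does not follow. Bias at the null needs unequal shares after matching, and the protocol reports none. The range of 0.88 to 1.12 rests wholly on assumed shares and risk ratios; the milder imbalance of 5% versus 10% gives 0.95 to 1.04. The direction depends on whether other-reason stays carry lower or higher mortality, which is also unknown.

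**What to change.** 1. In the Diagnostic Phase, tabulate admitting-diagnosis class (COVID-19/respiratory, other medical, surgical/trauma, obstetric) and its missingness by arm, before and after matching. This uses no outcome data.
2. If completeness is adequate, add the class to the Day 0 covariates in Table 3, to the propensity score model and to the balance check in Table 4, row 3. Use the admitting diagnosis and not a discharge diagnosis, so that nothing after Day T enters.
3. Add one sensitivity analysis of the primary hazard ratio restricted to COVID-19/respiratory admitting diagnoses.
4. State in section VIII that the primary cohort may also include stays for other reasons.

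The cost is one derived variable, one re-run and a sentence of text. A few DEX+ patients may lose a match within the caliper, and some COVID-19 admissions recorded under non-respiratory codes will be put in the wrong class.
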